2. INTRODUCTION

Zavegeptan (PF-07930207; formerly BHV-3500) is a selective, high-affinity, small molecule CGRP receptor antagonist that was approved by the FDA on March 9, 2023, for the acute treatment of migraine with or without aura in adults via IN administration.¹ Zavegeptan 10 mg nasal spray offers a novel IN CGRP receptor antagonist therapy for the acute treatment of migraine with the potential to address important unmet medical needs in the migraine patient population. IN zavegeptan provides rapid onset, durable efficacy without the risk of medication overuse headache and without contraindications or warnings regarding use by patients with cardiovascular disease.

CGRP is an endogenous 37 amino acid peptide contained within pain-signaling nociceptive afferents and is thought to play a causal role in migraine.^{2,3} Multiple lines of clinical evidence point to a role for CGRP in migraine pathophysiology: 1) serum levels of CGRP are elevated during migraine;⁴ 2) treatment with anti-migraine drugs returns CGRP levels to normal coincident with pain relief;⁵ and 3) IV CGRP infusion produces lasting pain in non-migraineurs and migraineurs.^{3,6}

Treatment with a CGRP receptor antagonist is thought to relieve migraine by: 1) blocking CGRP-induced neurogenic vasodilation (returning dilated intracranial arteries to normal); 2) halting the cascade of CGRP-induced neurogenic inflammation (which leads to peripheral and central sensitization); and/or 3) inhibiting the central relay of pain signals from the trigeminal nerve to the caudal trigeminal nucleus.^{2,7}

2.1. Study Rationale

As a component of zavegeptan clinical development, future pediatric studies will be conducted to evaluate the safety, tolerability, and PK of zavegeptan in participants 6 to less than 12 years of age with migraine. Recruiting and retaining pediatric patients in clinical trials has always been challenging due to a variety of factors, including inconvenience with patient preferences. To overcome some of those challenges, it is essential to prioritize patient-centric approaches that cater to the unique needs of pediatric patients. One such approach is PCS, which aims to reduce the burden on pediatric patients by minimizing the volume of the biological samples required and being less invasive with minimal pain compared to the venous phlebotomy collection method, which is particularly beneficial for pediatrics who are fearful of needles. Additionally, PCS offers greater flexibility to pediatric patients and their families by allowing at-home sample collection for those who may have difficulty traveling to clinics.

To allow the use of PCS in zavegeptan pediatric studies, a bridging or comparative study comparing the PCS approach with an equivalent conventional sampling technique is needed as a regulatory expectation to demonstrate the concordance of data from PCS in a controlled environment prior to implementation in large-scale clinical trials. Therefore, the primary objective of this study is to establish the correlation between zavegeptan concentration from samples collected using PCS devices compared to conventional venous blood sampling. In addition, if feasible, this study will also determine the PK and safety of zavegeptan IN in Japanese participants.

Lastly, based on data from zavegeptan IN clinical trials, dysgeusia (bad/metallic/bitter taste) has been reported as the most common treatment-emergent adverse event with zavegeptan. For instance, in a Phase 2/3, double-blind, randomized, placebo-controlled study (BHV3500-201^{8,9}), dysgeusia was reported as the most common TEAEs with zavegeptan 10 and 20 mg IN and placebo (13.5% to 16.1% vs 3.5%, respectively). Similarly, results from a Phase 3 study of zavegeptan IN administration for the treatment of acute migraine BHV3500-301¹⁰ have reported dysgeusia as the most common TEAEs after zavegeptan 10 mg IN administration with an incidence rate of 20.5% vs 4.7% in placebo. Because of this adverse event, patients may not adhere to their medications which may limit the effectiveness of treatment with zavegeptan. Therefore, understanding this adverse event (eg, time-course, description of the taste sensation) and potential strategies to mask the unpleasant taste could help improve patient experience and adherence. As an exploratory objective, this study will evaluate palatability attributes of zavegeptan and whether eating a butterscotch candy before zavegeptan IN administration will help manage dysgeusia.

2.2. Background

Migraine is a chronic neurological condition characterized by attacks of headache that usually feature unilateral, throbbing pain accompanied by nausea or sensitivity to light and sound.¹¹ Migraine affects about 1.04 billion people globally,¹² approximately three-quarters of whom are women. During migraine attacks, most people have functional impairments, often leading to absence from or reduced productivity at work or school and limiting participation in family, social, and leisure activities.¹³ Migraine-related disability extends to periods between attacks¹⁴ and can include physical symptoms (gastroparesis), which can slow absorption of oral drugs, and psychological symptoms (anger, anxiety, depression, hopelessness¹⁵). Persistent stigma about migraine¹⁶ leads many people to understate or under-report the negative effects of migraine and to avoid discussing their condition.¹⁴

The use of medication for the acute treatment of migraine attacks is ubiquitous.^{17,18} For the past 30 years, serotonin receptor agonists (ie, triptans) have been the most widely prescribed class of acute antimigraine medication. All 7 drugs in the triptan class are available for oral administration; two (sumatriptan and zolmitriptan) are available as nasal sprays and only sumatriptan is available for parenteral or rectal administration. Some non-oral therapies have shorter T_{max} than oral therapies;¹⁹ shorter T_{max} values might be associated with a more rapid onset of treatment effects.²⁰ The recommendation for the use of non-oral triptans is based on favorable pharmacokinetic profiles,^{19,20} a small set of comparative studies indicating that, for some agents, nasal formulations outperform tablets,^{21,22} and clinical practice experience.²³

Oral triptans provide a pain-free response in 20%–40% of patients with migraine and consistent benefits in 39%–79%.^{18,24,25,26} Yet recurrence rates range from 20% to 40% of patients with migraine, and clinical use is limited by cardiovascular contraindications and precautions, which are most common among men older than 40 years and postmenopausal women.^{18,24,25,26} Additionally, medication overuse is a recognized risk that can result in medication-overuse headache and the transformation of episodic migraine into chronic migraine.²⁵

Although alternatives to oral triptans have long been available, the findings that CGRP is a key element of migraine pathophysiology^{27,28,29} have resulted in the development of highly specific, safe,³⁰ and effective³¹ medications for acute treatment. Two small-molecule CGRP receptor antagonists (gepants) have received regulatory approval for the acute treatment of migraine in the USA: rimegeptan, an orally disintegrating tablet, and ubrogeptan, an oral tablet. Rimegeptan has also been approved for the acute treatment of migraine in the EU and the UK. This new class of agents attempts to address the limitations of acute treatment with traditional migraine medications, but neither drug is available in a non-oral formulation. Zavegeptan nasal spray is the first non-oral gepant approved for the acute treatment of migraine.¹ The clinical pharmacology of zavegeptan has been well characterized in a comprehensive program based on 10 Phase 1 studies.³² Efficacy and safety were determined in 2 positive pivotal trials assessing IN administration of zavegeptan for the acute treatment of migraine. A favorable safety profile was seen during a 1-year open-label safety study with up to 8 doses per month of IN zavegeptan for the acute treatment of migraine.³³

2.2.1. Nonclinical Overview

A summary of the nonclinical investigational programs can be found in the current IB.

2.2.2. Clinical Overview

2.2.2.1. Safety Overview

In clinical studies, approximately 2,700 participants have been administered zavegeptan IN, and approximately 606 participants have been administered oral zavegeptan. Administration of zavegeptan was well tolerated at 5 mg, 10 mg, and 20 mg as a single IN spray in 1,185 adult participants with migraine (BHV3500-201^{8,9}). A similar safety profile was observed in the 629 adult participants administered a single dose of zavegeptan 10 mg IN for the acute treatment of migraine (BHV3500-301¹⁰).

Zavegeptan, 10 mg IN, was well tolerated in a completed long-term safety study (up to 8 doses per month) in 603 adult participants with migraine for up to 52 weeks (BHV3500-202³⁴). The most frequently occurring adverse events in clinical studies to date have been associated primarily with IN administration (eg, dysgeusia, throat irritation, nasal congestion, nasal discomfort), as well as nausea and back pain, and the majority have been of mild to moderate intensity.

2.2.2.2. Efficacy Overview

In a Phase 2/3, double-blind, randomized, placebo-controlled, dose-ranging study of zavegeptan (5 mg, 10 mg, or 20 mg) IN for the acute treatment of migraine, zavegeptan doses of 10 mg and 20 mg via IN administration demonstrated statistically significant efficacy on both coprimary endpoints of freedom from pain at 2 hours postdose and freedom from MBS at 2 hours postdose.

A Phase 3 study of zavegeptan IN administration for the treatment of acute migraine (BHV3500-301¹⁰) demonstrated statistically significant efficacy for both coprimary endpoints

as well as for 13 of the 17 secondary endpoints, including significant evidence of ultrarapid onset and durability of response.

A Phase 2/3 study of oral zavegeptan in the preventive treatment of migraine (BHV3500-302) is currently ongoing.

2.2.2.3. Clinical Pharmacology

Based on the completed clinical studies of IN and PO zavegeptan, the following observations were made regarding the zavegeptan PK properties. Zavegeptan is rapidly absorbed (T_{max} : 0.54 hours) following a single zavegeptan 10 mg IN dose. The terminal elimination half-life of zavegeptan 10 mg IN dose is approximately 3 hours.³⁵ While the effective half-life of zavegeptan, which is considered more clinically relevant than the elimination half-life as it takes into account the entire plasma concentration-time profile, ranged from approximately 5 to 8 hours across dose levels ranging from 5 to 40 mg IN. Zavegeptan exhibits less than dose-proportional increases in exposure following single IN dose administration over the dose range from 1 mg to 40 mg. No evidence of meaningful accumulation was observed across a dose range of 5 to 20 mg zavegeptan IN after repeated QD dosing.

The results of the DDI study showed that co-administration of sumatriptan with zavegeptan IN does not result in a meaningful change in the PK of sumatriptan or of zavegeptan.

Co-administration of sumatriptan with zavegeptan IN does not cause elevations in mean arterial blood pressure or of systolic or diastolic blood pressure greater than those observed with sumatriptan alone. Lack of a clinically significant effect on the exposures of EE and LNG following co-administration of zavegeptan 20 mg IN and oral contraceptive support that zavegeptan is not a clinically relevant inhibitor of CYP3A4. Zavegeptan may be administered with an oral contraceptive without dose frequency adjustment. A 16% increase in the C_{max} and a 1.9-fold increase in zavegeptan AUC were observed in participants with moderate hepatic impairment.

Co-administration of itraconazole (strong CYP3A4 inhibitor and P-gp inhibitor) with IN zavegeptan showed no clinically relevant changes in the exposure of zavegeptan. However, co-administration of itraconazole with a single dose of zavegeptan oral soft gelatin capsule 50 mg increased the AUC and C_{max} of oral zavegeptan by approximately 59% and 77%, respectively, suggesting that the increase is likely due to P-gp inhibition of zavegeptan efflux transport by itraconazole in the gastrointestinal tract. In addition, coadministration of rifampin, a strong CYP3A inducer and an inhibitor of OATP1B3 and NTCP transporters with oral zavegeptan 100 mg, showed an increase in zavegeptan AUC by 2.3-fold and C_{max} by 2.2-fold in the presence of rifampin, suggesting that drugs that inhibit the OATP1B3 or NTCP transporters could increase the exposure of zavegeptan. Therefore, concomitant administration of zavegeptan with inhibitors of OATP1B3 or NTCP transporters should be avoided. Furthermore, it is unlikely that induction of CYP3A would substantially impact zavegeptan exposure when zavegeptan is administered either IN or oral. The 10 mg IN zavegeptan exposures were approximately 17% lower for C_{max} and 10% lower for AUC_{inf} during a migraine attack than in the non-migraine period; however, the decrease in exposure in the migraine state is not clinically meaningful. There was no clinically relevant prolongation of the QTc interval by zavegeptan.

2.3. Benefit/Risk Assessment

The safety and tolerability of zavegeptan doses greater than 10 mg IN were explored in early clinical development, including single doses of 0.1 mg through 40 mg and daily multiple doses up to 2 weeks ranging from 5 to 40 mg (refer to IB). Across these single and multiple dose ranges, zavegeptan was found to be generally safe and well tolerated.

The inclusion and exclusion criteria of this study have been chosen to select participants who are known to be free from any significant illness, history of autoimmune diseases, and any condition that could impact their safety or interfere with meeting the study objectives. The proposed safety screening and monitoring assessments are deemed to be sufficient to monitor the potential risks of zavegeptan administration. There is no anticipated therapeutic benefit for the healthy participants in this study.

More detailed information about the known and expected benefits and risks and reasonably expected AEs of zavegeptan may be found in the USPI¹ which is the SRSD for this study. Refer to the Study Intervention(s) table in Section 6.1 for a complete description of SRSDs.

2.3.1. Risk Assessment

Potential Risk of Clinical Significance	Summary of Data/Rationale for Risk	Mitigation Strategy
Study Intervention Zavegeptan		
Hypersensitivity reactions	Hypersensitivity reactions including facial swelling and urticaria have occurred with zavegeptan.	Site staff and participants are instructed throughout protocol and ICD to immediately report all AEs post-dosing for further management instructions.
AEs associated with IN administration, such as dysgeusia, throat irritation, nasal congestion and nasal discomfort.	The potential risks are based on AEs reported in studies of zavegeptan IN administration, and the majority have been of mild to moderate intensity.	Eligibility criteria have been selected to ensure that only appropriate participants are included in the study (see Section 5.1). Nasal inspection will be conducted on Day -1 (to exclude participants with mucosal erythema, congestion, septal defects etc), and 24 h (\pm 30 min) postdose per the SoA. AEs and clinical laboratory results will be monitored on an ongoing basis.
Study Procedures		
The study intervention will be administered intranasally via a liquid spray device.	The IN administration could be affected by some human and operational factors, such as the way of handling the devices and the way of inhalation and exhalation. These may lead to higher variabilities in PK data.	Enhanced site training and participant education in terms of the study intervention administration. For all the study participants, all attempts would be made for study intervention administration performed by no more than 3 study staff members to minimize variability in device handling.
Relatively intensive PK sampling and narrow time window within 1 hour post dose.	Risk of PK sample collection outside the required time window might be higher.	Enhance site communication and training. Actual PK sampling times will be used in the derivation of PK parameters.
Other		
Atypical PK sampling methodology (Tasso devices)	Risk of improper collection procedure that could lead to compromised sample(s)	Enhanced site communication and training on Tasso device collection and handling procedures

PFIZER CONFIDENTIAL

CT02-GSOP Clinical Pharmacology Protocol Template (14 April 2023)

Page 30

2.3.2. Benefit Assessment

Zavegeptan is not expected to provide any clinical benefit to healthy participants. This study is designed primarily to generate pharmacokinetic, safety, and tolerability data in healthy adults. As noted earlier, data from this study will be used to support the future clinical development of zavegeptan in pediatrics.

2.3.3. Overall Benefit/Risk Conclusion

Considering all available nonclinical and clinical data regarding the reassuring safety and tolerability of zavegeptan to date and measures to monitor and minimize risk to study participants in this study, the overall benefit/risk profile supports the further clinical development of zavegeptan in healthy adults.

3. OBJECTIVES AND ENDPOINTS

Objectives	Endpoints
Primary: 
Characterize the PK profile of zavegeptan from samples collected using Tasso Devices (Tasso-Plus and Tasso-M20) vs. standard venous phlebotomy following IN administration of 10 mg of zavegeptan IN formulation in healthy participants	Primary: 
Zavegeptan concentrations from samples collected using Tasso devices vs. standard venous phlebotomyPK parameters: AUC_{inf} (if data permit), AUC_{last}, C_{max}, T_{max}, $t_{1/2}$, CL/F and V_z/F, as data permits
Secondary: 
Evaluate the safety and tolerability following IN administration of 10 mg of zavegeptan IN formulation in healthy participants	Secondary: 
Assessment of TEAEs, and clinical safety laboratory tests
Tertiary/Exploratory: 
Evaluate the effect of the administration of 10 mg of zavegeptan IN with a butterscotch candy on dysgeusia compared to zavegeptan IN alone	Tertiary/Exploratory: 
Taste Assessment Survey Scoring Metrics after study intervention: overall liking, bitterness, tongue/mouth burn, throat burn, sour taste, salty taste, and sweet taste

4. STUDY DESIGN

4.1. Overall Design

This is a single-center, Phase 1, non-randomized, open-label, 2-period study in healthy participants to primarily evaluate the correlation of zavegeptan concentration from samples

PFIZER CONFIDENTIAL

CT02-GSOP Clinical Pharmacology Protocol Template (14 April 2023)

Page 31

collected using Tasso Devices (Tasso-Plus and Tasso-M20) compared to standard venous phlebotomy. This study consists of two periods which will include approximately 14 participants.

In period 1, 50% (n=7) of participants will use Tasso-Plus, while the other 50% (n=7) will use Tasso-M20. All 14 participants will have 6 PK samples collected using the assigned Tasso device simultaneously with collecting venous blood samples at the following time points, 30 minutes, 1, 2-, 4-, 8-, and 12-hour postdose, as described in the [SoA, Table 2](#). In addition, taste assessments will be performed at time intervals of 1 (immediately after dosing), 5, 10 and 20 minutes after zavegeptan IN administration. Also, if feasible, 4 Japanese participants will be enrolled among those 14 participants to evaluate the PK and safety of zavegeptan IN in Japanese vs. non-Japanese participants. For Japanese participants, a total of 12 venous blood samples will be collected at the following time points, 0, 15 minutes, 30 minutes, 1, 1.5-, 2-, 3-, 4-, 6-, 8-, 12-, and 24-hour (refer to [SoA, Table 2](#)).

In period 2, a butterscotch candy will be given 5 minutes before administering the zavegeptan IN study intervention. Taste assessment will also be performed after zavegeptan IN administration with a butterscotch candy in period 2. For taste assessment, each participant will record the sensory attributes at timed intervals of 1 (immediately after dosing), 5, 10 and 20 minutes after zavegeptan administration in each period.

Healthy participants will be screened within 28 days prior to the first administration of the study intervention to confirm that they meet the participant selection criteria for the study. Eligible participants will be admitted to the CRU on Day -1 and will be confined in the CRU until Discharge on Day 3 ([SoA](#)), approximately 24 hours after the second dose. Enrolled participants will receive a single IN dose of zavegeptan 10 mg (0.1 mL) in each period. PK venous blood samples as well as Tasso PK sampling, using Tasso-Plus and Tasso-M20, will be collected at specified intervals as per [SoA \(Table 2\)](#) for PK assessments.

The primary analysis will occur when all participants have PK samples collected. The expected duration of participation from screening until follow-up telephone contact is approximately 9 weeks.

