Alcohol breath, urine drug screening and urine cotinine testing	X	X						
 • Alcohol breath test will be performed at the discretion of the investigator. • Urine cotinine (mandatory) will be performed at Screening, and on Period 1 Day -1. This test may be performed at any other time at the discretion of the investigator.

PFIZER CONFIDENTIAL

CT02-GSOP Clinical Pharmacology Protocol Template (14 April 2023)

Table 1. Study Schedule of Assessment

Visit Identifier Abbreviations used in this table may be found in Appendix 12 .	Screen	Period 1		Period 2		Telephone F/U	Early Discontinuation	Notes
Days Relative to Day 1	Day - 28 to Day -2	Day - 1	Day 1	Day 2	Day 3	Day 30-37		
 • All screening should be done \leq28 days before the first dose. • Day relative to start of study intervention (Day 1). • Follow-up may occur via telephone contact and must occur 28-35 days after administration of the final dose of study intervention.
Days within each period		Day - 1	Day 1	Day 1	Day 2			
HIV, HBsAg, HBsAb, HBcAb, HCVAb	X							
 • HBsAb is to be run if HBsAg and/or HBcAb are positive.
Retained Research Sample for Genetics (Prep D1)			X					
Study intervention administration			X	X				
PK blood sampling			X	X			X	
 • See Table 2 for details. • Period 2 Day 1 PK sample will be 24 hr post dosing in Period 1 Day 1. Sample will be collected for Japanese participants only.
CRU discharge					X			
 • Discharge from CRU after completing protocol-required activities on the day.
Serious and nonserious AE monitoring	X	→	→	→	X	X	X	
 • See Section 8.4.3 for follow-up AE and SAE assessments.

Table 2. Pharmacokinetic Sampling Timepoints

Visit Identifier												Notes
Study Day	Day 1										Day 2	
Days within each period	Period 1, Day 1										Period 2, Day 1	
Time Before/After Dose	0 h	0.25 h	0.5 h	1 h	1.5 h	2 h	3 h	4 h	6 h	8 h	12 h	24 h
Study intervention administration	X											
Venous PK sampling	X ^b	X ^b	X	X	X ^b	X	X ^b	X	X ^b	X	X	X ^b
Tasso PK sampling ^a			X	X		X		X		X	X	
Blood: plasma ratio				X					X			

a. Tasso PK sampling will be performed using either Tasso-Plus or Tasso-M20 device.

b. To be collected for Japanese participants only.

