A healthy participant population is considered for the study because healthy participants with no concomitant diseases and using no concomitant medications represent a homogenous population allowing for proper evaluation of the PK, safety, and tolerability of a drug without confounding factors. Six PK samples will be collected from the Tasso devices at the same time of collecting venous blood samples, as described in the [SoA, Table 2](#). Those 6 Tasso-venous paired samples collected in 7 participants for each device ($7 \times 6 = 42$ data points) are sufficient to meet the scientific community recommendation for having an adequate Tasso-venous phlebotomy PK bridging study.³⁶ Different PK sampling times were selected to cover the concentration-time profile of zavegeptant IN. Of note, blood-to-plasma ratio samples will be aliquoted from the same venous blood draw as specified in the [SoA, Table 2](#). These samples will be crucial for determining the blood-to-plasma ratio value for each participant to convert the dried blood concentrations collected using Tasso-M20 to their equivalent plasma concentrations for adequate comparison between the 2 methods.

If feasible, 4 Japanese participants will be enrolled among the 14 participants planned for this study to determine the PK and safety of zavegeptant IN in this population since there is no PK and safety data available for the use of zavegeptant IN in this population. Leveraging this data will be useful in supporting the development of zavegeptant IN in Japan. However, the recruitment of these Japanese participants will be optional, and the completion of this trial will not require their enrollment.

As noted earlier, data from clinical trials of zavegeptant IN formulation have shown dysgeusia (bad/metallic/bitter taste) as the most common treatment-emergent adverse event following zavegeptant administration (refer to IB). We hypothesize that the mechanism of dysgeusia associated with zavegeptant nasal spray administration relates to the postnasal dripping of residual spray into the oral cavity and contact with the posterior tongue and taste buds, triggering the taste receptor cells. To test this hypothesis and better understand this adverse event (its intensity, onset, and duration), a taste assessment questionnaire will be performed at 1 (immediately after dosing), 5, 10 and 20 minutes after zavegeptant IN administration.

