6.1.2. Zavegepant PK Parameters

The PK parameters of zavegepant will be listed and summarized descriptively for each collection method (Tasso-Plus, Tasso-M20 and venous phlebotomy), and by race (non-Japanese and Japanese), as data permits for the PK Parameter Analysis Set. Each zavegepant PK parameter will be summarized including the set of summary statistics as specified in Table 3.

For AUC_{last} , AUC_{inf} , and C_{max} , box and whisker plots for individual participant parameters will be constructed for each collection method and overlaid with geometric means.

Table 3. PK Parameters to be Summarized Descriptively by Collection Method and Race

Parameter	Summary Statistics
AUC_{inf} , AUC_{last} , C_{max} , CL/F , V_z/F	N, arithmetic mean, median, SD, %CV, minimum, maximum, geometric mean and geometric %CV
T_{max} , T_{last}	N, median, minimum, maximum
$t_{1/2}$	N, arithmetic mean, median, SD, %CV, minimum, maximum

Supporting data from the estimation of $t_{1/2}$ and AUC_{inf} will be listed by collection method and by race: terminal phase rate constant (k_{el}); goodness of fit statistic from the log-linear regression (r^2); the percent of AUC_{inf} based on extrapolation ($AUC_{extrap}\%$); and the first, last, and number of time points used in the estimation of k_{el} . This data may be included in the clinical study report.

For the Tasso vs. Venous comparison, natural log-transformed zavegepant AUC_{inf} (if data permit), AUC_{last} and C_{max} will be analyzed using a mixed effect model with blood collection method as fixed effect and participant as random effect. Estimates of the adjusted mean differences (Test – Reference) and corresponding 90% CIs will be obtained from the model with Venous as the Reference group and Tasso-M20 (or Tasso-Plus) as the Test group. The adjusted mean differences and 90% CIs for the differences will be exponentiated to estimate the adjusted geometric means ratio (Test/Reference) and 90% CIs for the ratios.

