For race comparison, natural log-transformed zavegepant AUC_{inf} (if data permit), AUC_{last} and C_{max} will be analyzed using an ANOVA model with race as fixed effect. Estimates of the adjusted mean differences (Test – Reference) and corresponding 90% CIs will be obtained from the model with non-Japanese as the Reference group and Japanese as the Test group. The adjusted mean differences and 90% CIs for the differences will be exponentiated to estimate the adjusted geometric means ratio (Test/Reference) and 90% CIs for the ratios.

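### If Japanese participants enrol, SAP 6.1.2 compares Cmax over unequal sampling schedules: the race ratio is biased slightly up, the Tasso/venous ratio slightly down

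*Protocol*

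**What the plan says.** **Sampling.** Protocol 4.1 has all participants sampled by Tasso and vein together at "30 minutes, 1, 2-, 4-, 8-, and 12-hour postdose". It then adds: "For Japanese participants, a total of 12 venous blood samples will be collected at the following time points, 0, 15 minutes, 30 minutes", with the list running on through 1, 1.5, 2, 3, 4, 6, 8, 12 and 24 hours. Protocol 1.3, Table 2, marks the venous samples at 0, 0.25, 1.5, 3, 6 and 24 h with a footnote: "To be collected for Japanese participants only". No Tasso sample is scheduled at any of those times.

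**Numbers.** Protocol 4.2: "If feasible, 4 Japanese participants will be enrolled among the 14 participants planned for this study". The same section says that "the recruitment of these Japanese participants will be optional".

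**Derivation.** Protocol Table 3 and SAP Table 2 take Cmax as the largest observed concentration and Tmax as the time at which it first occurs.

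**Comparison.** For race, SAP 6.1.2 says that log-transformed AUCinf, AUClast and Cmax "will be analyzed using an ANOVA model with race as fixed effect". For Tasso against vein, the same parameters "will be analyzed using a mixed effect model with blood collection method as fixed effect and participant as random effect". Both give a ratio with a 90% CI. Tmax appears only in SAP Table 3 ("PK Parameters to be Summarized Descriptively by Collection Method and Race"), as N, median, minimum and maximum.

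**What is absent.** SAP 3.1.2, 5.3.1 and 6.1.2 contain no rule limiting Cmax or Tmax to times that all profiles share. SAP 5.3.1 deals with values below quantification, missing values and anomalous values, not with unequal schedules. SAP 6.3 plans no subset analyses.

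**The concern.** An observed maximum depends on how often one looks. A profile sampled 11 times has more chances to catch a high value than one sampled six times, whether because the true peak falls between the sparse times or because assay and sampling scatter throws up a high reading. The extra looks belong to one group (Japanese) and one method (venous), so the difference in schedule is confounded with both contrasts that SAP 6.1.2 estimates.

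Cmax is a listed primary endpoint. The race contrast is meant to support development in Japan, and the device contrast to support Tasso in paediatric studies. Part of a higher Japanese peak, or of a lower Tasso peak, could be nothing but the schedule. Nor does the protocol say how Japanese participants are to be spread over the two devices, so the artefact could fall mainly on one device and look like a difference between devices.

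**Working it through.** **1. Counting the samples**

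| Profile | Post-dose times (h) | Number |
|---|---|---|
| Japanese venous | 0.25, 0.5, 1, 1.5, 2, 3, 4, 6, 8, 12, 24 | 11 |
| Non-Japanese venous | 0.5, 1, 2, 4, 8, 12 | 6 |
| Tasso, everyone | 0.5, 1, 2, 4, 8, 12 | 6 |

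Adding the pre-dose sample gives the protocol's 12 Japanese venous samples. The sample-size figure also reproduces: 7 participants x 6 pairs = 42 per device. Protocol 9.5 gives no precision for Cmax or Tmax.

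**2. Direction for Cmax**

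The six shared times are a subset of the 11, so for any one venous profile max(11 times) >= max(6 shared times). With no true difference:
- the expected log Cmax ratio, Japanese to non-Japanese, is zero or above;
- within a Japanese participant, the expected log ratio of Tasso to venous is zero or below;
- within a non-Japanese participant it is zero, because both methods use the same times.

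None of this depends on a PK model.

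**3. Size: inputs**

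- From protocol 4.2: Tmax 0.54 h; half-life about 3 h (elimination) or 6.55 h (effective).
- Assumed, because the documents give no figures: one compartment with first-order absorption, elimination-rate CV 25%, absorption-rate CV 30, 60 or 100%, and independent scatter per sample of 0, 10 or 20%.

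*Typical profile without scatter.* For a half-life of 3 h, ke = ln 2 / 3 = 0.231 per h. Solving ln(ka/ke)/(ka - ke) = 0.54 gives ka = 6.37 per h. Concentrations as a fraction of the true peak are then 0.871 at 0.25 h, 0.999 at 0.5 h, 0.931 at 1 h and 0.831 at 1.5 h. The 0.5 h sample, which everyone has, is the maximum on both schedules, so the ratio is 1.00. Any bias comes from variation between participants and from scatter.

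**4. Race ratio for Cmax**

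Simulation with 100,000 profiles per setting and 18 settings (2 half-lives x 3 absorption CVs x 3 scatter levels). The ratio is exp(mean[log max over 11 times - log max over 6 times]).

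| Scatter per sample | Ratio with no true difference |
|---|---|
| 0% | 1.000-1.011 |
| 10% | 1.015-1.032 |
| 20% | 1.045-1.062 |

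Sensitivity at half-life 3 h: a true Tmax of 0.35 h gives 1.01-1.08; 0.75-1.0 h gives 1.00-1.06.

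**5. Tasso/venous ratio for Cmax**

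Within Japanese participants the simulated ratio is 0.94-1.00, with 0.942 at the low end. With complete pairs, the mixed-model estimate for a device is essentially the mean within-participant log difference. If k of n participants are Japanese, the ratio is therefore 0.942^(k/n) at worst:
- 4 of 14 pooled, or equally 2 of 7 in each device: 0.942^(2/7) = 0.983;
- all 4 in one device group of 7: 0.942^(4/7) = 0.966;
- none: 1.00.

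**6. Tmax**

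Moving from the six shared times to the 11, Tmax is earlier in 3-28% of profiles, unchanged in 61-97% and later in 0-17%. The median is unchanged in all but one of the 18 settings, and the mean moves by -0.06 to +0.02 h. With a true Tmax of 0.75-1.0 h the mean usually moves later (from 0.02 h earlier to 0.12 h later), because the 1.5 h and 3 h samples are also Japanese-only.

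**7. Against the precision of the race comparison**

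For 4 versus 10 participants the 90% half-width on the log scale is t(0.95, 12 df) x s x sqrt(1/4 + 1/10) = 1.782 x s x 0.592, with s = sqrt(ln(1 + CV^2)). Assuming a between-participant Cmax CV of 30%, s = 0.294 and the interval around a ratio of 1 is 0.73-1.36. At 60%, s = 0.555 and it is 0.56-1.79.

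**The case against.** The strongest reply is that little turns on this.

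- No hypothesis is tested and neither document sets an acceptance range for the ratios. A shift of 0-6% inside an interval of about 0.73-1.36 or wider will not change how the race result is read. This stands, and it keeps the point modest.
- The main bridging evidence is the correlation and Bland-Altman analysis of concentrations drawn at the same moment (SAP 6.1.1). Those pairs exist only at the six shared times, so they are untouched. This stands.
- The issue is conditional. Japanese enrolment is optional, and SAP 6.1.2 does not say which method's parameters feed the race ANOVA. With no Japanese participants, or with Tasso profiles only, the race bias does not arise. This stands.
- The extra early samples were chosen to capture rapid absorption, and dropping them from the comparison loses information. This is true, but they can still be reported for the Japanese group, and a comparison needs like with like.

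Two stronger readings are tempting and should not be drawn. A reader might infer that the schedule alone makes Japanese participants look faster to peak. The documents do not support that: an observed Tmax of 0.25 h is possible only in their venous data, but the 1.5 h and 3 h samples can move Tmax later, and no Tmax ratio or interval is planned. A reader might also infer that Tasso in general will read low against vein. Only the Japanese participants, at most four as planned, contribute to that; for everyone else the two methods share every time point.

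What the reply does not answer is why maxima over different sets of times should be compared at all, when the remedy needs no new data.

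**Conclusion.** The concern holds in limited form. If Japanese participants enrol and their venous profiles feed the race ANOVA, the Cmax comparisons in SAP 6.1.2 carry a bias of known direction that comes from the schedule alone. More participants would not remove it, and neither would cutting every profile at 12 h.

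Its size is small: about 1.00-1.06 for the race ratio at the protocol's Tmax of 0.54 h, about 0-2% for Tasso/venous pooled over 14, and up to about 3% in a device group holding all four Japanese participants. The direction for Cmax follows from the schedules. The magnitudes rest on the assumed one-compartment model and variability, and most of the effect depends on the assumed sample scatter. Tmax values from the two schedules are not comparable, but the shift can go either way. This is a correction worth making before analysis, not a threat to the trial.

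**What to change.** In SAP 3.1.2 and 6.1.2, state that Cmax for the race ANOVA and the Tasso/venous mixed model, and the Tmax shown in the by-race and by-method tables, are derived from the six shared nominal times only (0.5, 1, 2, 4, 8 and 12 h). State also which collection method feeds the race ANOVA. Report Japanese venous Cmax and Tmax from the full schedule in a separate summary, labelled as description and not as a comparison.

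For Cmax this sets the schedule effect to zero by construction: with no true difference the expected ratios are 1.00 for both race and method. Tmax is then read from the same times in every profile.

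The cost is SAP wording and one extra derivation on data already planned; no samples or visits change. The downside is small: the comparison does not use the extra Japanese samples, although they remain in the separate summary.
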